4.2 Drug Accountability

The Investigational Pharmacist will manage drug accountability records for temsirolimus. Sorafenib will be procured from commercial supplies and accounted for according to standard of care.

4.3 Drug Ordering

Sorafenib will be ordered as a standard of care medication and will be obtained from commercial supplies.

Temsirolimus will be supplied for this trial directly by the manufacturer, Pfizer, Inc., from commercial supplies. Temsirolimus will be shipped directly to the primary study site: UCSF Helen Diller Family Comprehensive Cancer Center, and to the study sub-site: Robert H. Lurie Comprehensive Cancer Center of Northwestern University. Both sites will be responsible for direct distribution of the drug to the study patients and for drug accountability at each respective site.

To obtain temsirolimus study drug supply or for questions about temsirolimus supply, each site will contact Pfizer, Inc. directly: [REDACTED] [REDACTED]

At the conclusion of the study, each institution will promptly contact the individual identified above at the research grant provider (Pfizer, Inc.) for instruction regarding whether to return all unused temsirolimus and associated diluent at the research grant provider's expense, or whether to dispose properly of temsirolimus and associated diluent at its own expense and submit documentation of such destruction. The determination as to whether the study drug shall be returned or destroyed is solely within the research grant provider's discretion.

4.4 Packaging and Labeling of Study Drugs

Drugs will be packaged and labeled per UCSF institutional standards, adhering to applicable local and federal laws.

5. Treatment Plan

5.1 Dosage and Administration

Treatment will be administered on an outpatient basis.

Temsirolimus at a dose of 10 mg weekly will be administered intravenously over 60 minutes using an infusion pump in the study site infusion center starting on Cycle 1, Day 1 of study enrollment. Infusion will be given through non-DEHP-containing tubing with an in-line polyethersulfone filter (≤ 5 microns). Premedication with diphenhydramine 25-50 mg IV will be administered 30 minutes prior to each temsirolimus infusion. Patients will be monitored by infusion center nursing staff every 15 minutes during infusion, with treatment interruption required for any evidence of an infusion reaction. If hypersensitivity symptoms develop, infusion will be stopped. Patients will be treated with additional H1 antagonist as well as an H2 antagonist (such as famotidine 20 mg or ranitidine 50 mg intravenously) at discretion of treating investigator. If hypersensitivity symptoms are mild (Grade 1 or 2) and resolve over 30-60 minutes of observation and with administration of additional H1 and H2 blocker, infusion may resume with caution at a reduced rate (over approximately 60 minutes), at the discretion of the treating investigator. Additional supportive care measures will be available in each study site infusion center in case of severe hypersensitivity reaction. Temsirolimus dosing will continue weekly (± 3 days) until unacceptable toxicity, disease progression, the withdrawal of consent by the patient, or the decision to discontinue treatment by the treating physician. Subsequent infusions starting Cycle 2, Day 1 may be given over 30 minutes if no evidence of infusion reaction is observed after the first cycle has been completed.

Patients will be instructed to take sorafenib at starting dose of 200 mg 1 tab twice daily starting on Cycle 1, Day 1 of study enrollment after completion of temsirolimus infusion. Sorafenib will be ingested with water on an empty stomach, either 1 hour before or 2 hours after food ingestion. If unable to tolerate sorafenib on an empty stomach, it may be taken with a low fat meal. The tablet will be swallowed whole. Sorafenib dosing will continue daily or twice daily without interruption until unacceptable toxicity, disease progression, the withdrawal of consent by the patient, or the decision to discontinue treatment by the treating physician (*see Section 6.3 Reasons to Withdraw a Subject*).

Table 5.1 Regimen Description

Study Drug	Premedication; precautions	Dose	Route	Schedule	Cycle Length
Temsirolimus	Premedicate with diphenhydramine 30 minutes prior to temsirolimus infusion; monitor every 15 minutes during infusion; administer with in-line filter	10 mg	IV	Weekly(± 3 days)	4 weeks (28 days)
Sorafenib	Take on empty stomach or with low fat meal	200 mg	Oral	BID	

5.2 Dose Modifications and Dosing Delays

The following adjustments should be made in the appropriate drug (depending on attribution of toxicity) based upon the guidelines below in *Section 5.2.3 Dose Modification Protocol*. If either study drug is discontinued, a patient will be removed from study.

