3.5 Duration of Follow Up

After treatment discontinuation, follow up for overall survival monitoring will be performed as described in *Section 6.1 Schedule of Procedures and Observations* for up to 5 years or until death, whichever comes first. The study will end 5 years after the final patient discontinues treatment or after all patients are deceased, whichever comes first.

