6.1.6 Long Term/Survival Follow-up Procedures

Patients will be followed every 3-6 months (\pm 3 months) for up to 5 years after study discontinuation or until death, whichever comes first.

The following procedures will be performed at standard-of-care clinic visits with treating investigator or by telephone calls from treating investigator or a designated study coordinator (\pm 2 months):

- Evaluation of clinical response or deterioration.
- Overall survival will be measured from time of first dose of protocol therapy to date of death; for patients who are lost to follow up, survival will be censored at date last known to be alive.
- Evaluation of any residual symptomatic adverse events (if applicable).
- Other anti-cancer therapies.

Table 6.1 Schedule of Study Procedures and Assessments

Period/Procedure	Screening	Cycle 1				Cycle 2 and future Cycles				End of Treatment visit	Follow Up Visit*
Study Day/Visit Day	-28 to 1	1	8	15	22	1	8	15	22		
Informed consent	X										
Archival Specimen Collection ¹	X										
AE assessment		X	X	X	X	X				X	X
Concomitant medications	X ²	X	X	X	X	X				X	
Treatment/Drug Administration											
Temsirolimus ¹⁷		X	X	X	X	X	X	X	X		
Sorafenib ³		X	X	X	X	X	X	X	X		
Clinical procedures											
Physical exam	X	X	X	X	X	X				X	
Vital signs	X	X	X	X	X	X	X ⁴	X	X	X	
Medical history	X									X	X ⁶
Liver disease assessment ⁵	X										
Performance Status	X					X				X	
Laboratory procedures											
Hematology (CBC w/Diff)	X	X	X	X	X	X	X	X	X	X	
Blood chemistry ⁷	X	X	X	X	X	X	X	X	X	X	
Coagulation ⁸	X	X	X	X	X	X	X	X	X	X	
AFP		X				X				X	
HCV, HBV sAb, HBV sAg, HBV cAb total & IgM ¹⁶	X										
Hemoglobin A1c	X										
Hepatitis B viral DNA quantitative by PCR ⁹	X ⁹					X ⁹				X ⁹	
Fasting total cholesterol, triglycerides, and blood glucose ¹⁰	X ¹⁰					X ¹⁰					

Table 6.1 Schedule of Study Procedures and Assessments

Period/Procedure	Screening	Cycle 1				Cycle 2 and future Cycles				End of Treatment visit	Follow Up Visit*
Study Day/Visit Day	-28 to 1	1	8	15	22	1	8	15	22		
Standing phosphate repletion ¹¹	X ¹¹	X ¹¹				X ¹¹					
CTC ¹²		X ¹²				X ¹²					
Banking blood samples ¹³		X ¹³	X ¹³			X ¹³				X ¹³	
Pregnancy test (HCG)	X										
Imaging procedures											
Imaging (CT or MRI)	X					X ¹⁴				X ¹⁵	

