9.1.2 Primary Endpoint

Median TTP will be calculated in months from date of first dose of protocol therapy to date of removal from study for radiographic (per RECIST 1.1) and/or clinical progression including death attributed to progression. For patients removed from study for other reasons than progression (such as toxicity, withdrawal of consent, or death from other causes than documented radiographic and/or clinical progression), TTP will be censored at the date last known to be progression-free.

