9.2 Determination of Sample Size and Accrual Rate

9.2.1 Sample Size and Power Estimate

The sample size for this phase II study will be 25 patients under the assumption that the time to progression is approximately exponentially distributed and patients come onto study uniformly

during the study accrual. A sample size of 25 evaluable patients will have sufficient power to detect the difference between the null hypothesis that the median TTP is less than 3 months (based on historical controls) and the alternative hypothesis that the median TTP is more than 6 months. The study will have a 1-sided significance level of 10% and a power of 88% under the exact test for comparison of the TTP rates between $p_0 < 25\%$ versus $p_1 > 50\%$ at 6 months.

A median TTP of > 6 months would constitute a meaningful outcome in advanced HCC, based upon the benchmarks of first-line TTP of 5.5 months in the SHARP study and 2.8 months in the Asia-Pacific study.(Llovet, Ricci et al. 2008; Cheng, Kang et al. 2009) If median TTP is > 6 months in this study, a randomized phase II trial to compare the combination therapy to single-agent sorafenib should be considered. Such a trial would be much larger and more costly, however, and should not be undertaken prior to the current study to confirm that there is tolerability and a signal of efficacy to warrant proceeding with the larger trial, noting in particular the challenges to accrual in first-line HCC studies historically, as faced by contemporary cooperative group studies CALGB 80802 and ECOG 1208.

Accrual of 25 paired archival tumor and blood specimens also constitutes a meaningful endpoint in that it will enable future biomarker studies in subsets of patients with radiographic response, AFP response, prolonged stable disease, and primary progression, including potential exploratory studies for association with tissue biomarkers of mTOR pathway activation (such as pS6 staining).(Villanueva, Chiang et al. 2008)

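### Patients taken off study before about month 6 for reasons other than progression usually have no known 6-month progression status, and their later progression cannot count towards TTP

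*Combined protocol and SAP*

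**What the plan says.** - **Removal.** Section 5.2: "If either study drug is discontinued, a patient will be removed from study". Section 5.3 repeats the rule for protocol therapy. It also removes patients after a toxicity hold of more than 28 days, unless the Study Chair approves resumption.
- **Imaging.** Scans are done every 8 weeks on study. Section 6.1.4 adds one at end of treatment, within a 60-day window, only if none was done in the preceding 8 weeks. The follow-up column of Table 6.1 has no imaging.
- **Later follow-up.** Section 3.5: "After treatment discontinuation, follow up for overall survival monitoring will be performed". Section 6.1.6 sets contacts every 3 to 6 months: "The following procedures will be performed at standard-of-care clinic visits with treating investigator or by telephone calls". These contacts cover clinical status, residual toxicity and other anti-cancer treatment, but not scan results.
- **TTP.** Sections 2.4.1, 7.1.2 and 9.1.2 date the event by removal from study for progression. For other removals, 9.1.2 (like 2.4.1) says "TTP will be censored at the date last known to be progression-free", whereas 7.1.2 censors at the date the patient comes off study.
- **Powered analysis.** Section 9.2.1: "A sample size of 25 evaluable patients will have sufficient power to detect the difference", with a "1-sided significance level of 10% and a power of 88% under the exact test" "for comparison of the TTP rates between" 25% and 50% at 6 months. Sections 3.2 and 9.4.1 treat every eligible dosed patient as evaluable and do not replace them. Section 9.4.2 reports the 6-month proportion without saying how a patient censored earlier enters it.

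**The concern.** The go/no-go question is whether enough of 25 patients are progression-free at 6 months, judged against fixed historical values. A binomial test needs a yes or no for each patient. A patient who stops a drug for toxicity at month 3 supplies neither, and the event definition means that progression found at month 5 cannot be entered even if the site learns of it at a planned contact.

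The censoring may also be related to prognosis. Removal triggers in 5.2.3 and 5.2.4 include Grade 4 bilirubin, ascites that recurs despite reductions of both drugs, and recurrent Grade 3 haemorrhage. Section 1.2.1.1 reports that Child-Pugh B patients on sorafenib had more hyperbilirubinaemia and encephalopathy and a median OS of 3.2 months, against 9.5 for Child-Pugh A; B7 patients are eligible here. If those removed would have progressed sooner, Kaplan-Meier TTP reads too long. No estimator can restore progression that was never recorded.

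**Working it through.** **Inputs from the plan.** n = 25; one-sided alpha 10%; 6-month rates 25% and 50%; and the assumption in 9.2.1 that "the time to progression is approximately exponentially distributed". Medians of 3 and 6 months then give 0.5^(6/3) = 0.25 and 0.5^(6/6) = 0.50. The increase from 25 to 28 patients (25/0.90 = 27.8) covers ineligibility only.

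**Assumed, because the documents give no figure.** A fraction f = 10%, 20% or 30% leaves without progression at a time L uniform over months 0 to 5. Their progression hazard after leaving is r = 1, 1.5 or 2 times that of the rest.

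**1. The plan's own figure.** With success at 10 or more of 25:
- alpha = P(X ≥ 10 | 25, 0.25) = 7.1%
- power = P(X ≥ 10 | 25, 0.50) = 88.5%

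A cut-off of 9 gives alpha 14.9%, so 10 is the smallest that qualifies. The stated 88% reproduces if all 25 statuses are known.

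**2. How many statuses are missing.** At a 6-month median, a leaver is still progression-free at L with probability 2^(−L/6). Its mean over 0 to 5 months is 0.76. The unknown share is 0.76 × f = 7.6%, 15% or 23%, or about 2, 4 or 6 of 25.

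**3. Power with k unknown.** The plan gives no rule, so the possible conventions are set side by side. Unknown status is taken as independent of outcome.

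| k | Excluded, cut-off reset to alpha ≤ 10% | Power | Counted as failures: P(X ≥ 10 given 25, 0.5(1 − k/25)) |
|---|---|---|---|
| 0 | 10 of 25 | 88.5% | 88.5% |
| 2 | 9 of 23 | 89.5% | 78.8% |
| 3 | 9 of 22 | 85.7% | 72.5% |
| 5 | 9 of 20 | 74.8% | 57.5% |
| 6 | 8 of 19 | 82.0% | 49.3% |

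The exclusion column jumps because the test is discrete. Averaged over a Binomial(25, q) number of known statuses, with q = 0.925, 0.85 and 0.77, power is 86.1%, 82.4% and 78.0%. These averages are on the favourable side: early progressors keep their status and early leavers lose theirs, so at f = 30% and r = 1 the rate among known statuses is 0.45 against a true 0.50. Counting unknowns as successes instead raises true alpha to P(X ≥ 10 | 25, 0.25 + 0.75k/25) = 22% at k = 2 and 58% at k = 5.

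**4. Kaplan-Meier bias at 6 months.** Before leaving, everyone has the same hazard, so Kaplan-Meier estimates 0.50. The true rate is (1 − f) × 0.50 + f × S, where S = 2^(−r) × mean of 2^((r−1)L/6).
- r = 1: S = 0.50, so the bias is 0 at every f.
- r = 1.5: S = 0.354 × 1.159 = 0.410. At f = 30% the truth is 0.350 + 0.123 = 0.473, a bias of 2.7 points.
- r = 2: S = 0.25 × 1.354 = 0.338. At f = 30% the truth is 0.350 + 0.102 = 0.452, a bias of 4.8 points. At f = 20% it is 3.2 points and at f = 10% 1.6 points.

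Simulation with 1,000,000 patients per setting agrees. Under a different assumption (only a 30% frail subgroup can be removed, with 1.5 to 2 times the hazard throughout), a true median of 6 months reads 6.2 to 6.9. Three times the hazard takes it to 7.6 months, or 7 points at 6 months.

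**The case against.** Four points limit the concern, and each stands in part.

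- **Follow-up does not end at the last dose.** End of treatment is the day of the decision to stop participation and may fall after the last dose, and a scan can follow within 60 days. A patient removed in months 4 to 6 may obtain a 6-month status that way, and later removals already have one. A reader might infer that such patients never get a status; the text supports only that those removed before about month 6 usually do not.
- **Some hepatic decline will be an event.** TTP includes clinical progression and death attributed to progression, so ascites or a bilirubin rise judged to be tumour-related need not be censored. How often attribution goes the other way is unknown.
- **TTF is already planned.** It counts toxicity removals as failures, and 9.4.3 reports its 6-month proportion alongside TTP. The gap between the two shows the worst case for toxicity removals, but recovers no progression dates and still censors withdrawals.
- **The size is assumed and modest.** Five points is about half the standard error of a 50% rate with 25 patients, √(0.5 × 0.5/25) = 10 points. Two dose reductions per drug and permitted holds limit early removal. Excluding unknown statuses is not the plan's rule and sits badly with 3.2 and 9.4.1.

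None of this supplies a 6-month status for a patient removed at month 2 or 3, or a rule for one.

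**Conclusion.** The gap is real: no scheduled imaging after a conditional end-of-treatment scan, an event definition that shuts out later progression, two different censoring dates, and no rule for unknown status in the powered test. The 88% power is conditional on 25 known statuses. With 2 to 6 unknown it is roughly 86% to 78% if they are excluded (averaged) and 79% to 49% if they count as failures.

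A reader might go further and conclude that TTP censoring is informative and the result biased upwards. The documents do not show that. Liver dysfunction is linked there to both toxicity and shorter survival, which makes it plausible; but the bias is zero if those removed progress at the same rate, and about 5 points takes 30% leaving and a doubled hazard. Both the share leaving and the hazard ratio are assumptions. The phase I toxicity rates in 1.2.3.1 make removals likely but are not discontinuation rates, and the 75% TTP-evaluable figure in 9.4.4 concerns the biomarker set. The point is worth acting on because a few unknown statuses among 25 could decide whether a randomised trial follows, and the remedy is cheap.

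**What to change.** 1. **Sections 3.5 and 6.1.6.** For patients removed for reasons other than progression, record at the contacts already planned the date and result of any standard-of-care tumour imaging, until progression, a new anti-cancer therapy, death or withdrawal of consent.
2. **Sections 2.4.1, 7.1.2 and 9.1.2.** Define the TTP event by the date of progression, including progression on those scans, instead of by removal for progression. Use one censoring rule throughout: the last adequate tumour assessment before any new therapy.
3. **State in advance** whether continuing one of the two study drugs commercially after removal counts as new therapy. Sorafenib is obtained as standard of care, so this will arise. If it counts, such patients are censored early; if not, TTP includes time on a single agent.
4. **Section 9.4.2.** Say how a patient whose 6-month status is still unknown enters the exact test, and report on-study-only TTP as a sensitivity analysis beside TTF.

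The cost is a form field and retrieval of scan reports. No scans are mandated, and dosing and removal rules are unchanged. The downsides are that routine scans come at irregular times, so progression dates will be less even than on the 8-week schedule, and that little is gained for patients who switch therapy at once.

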5.2.1 Temsirolimus Dose Modifications

Patient Temsirolimus Dose Level	Temsirolimus Dose Modification
10 mg IV weekly (starting dose)	↓ to 7.5 mg IV weekly
7.5 mg IV weekly	↓ to 5 mg IV weekly
5 mg IV weekly	Discontinue

5.2.2 Sorafenib Dose Modifications

Patient Sorafenib Dose Level	Sorafenib Dose Modification
200 mg PO BID (starting dose)	↓ to 200 mg QD
200 mg PO QD	↓ to 200 mg PO QOD
200 mg PO QOD	Discontinue

5.2.3 Dose Modification Protocol

- Held doses of either drug will be considered as omitted. (For example, if temsirolimus is held on cycle 2, day 8, the next dose of temsirolimus the following week will be considered cycle 2, day 15, rather than delaying the cycle and repeating the day 8 dose.)
- Laboratory values should be rounded to one significant digit.
- For any toxicity (regardless of grade), despite optimal supportive care, that is felt by the treating investigator to represent a risk to the patient's safety, additional dose reduction,

treatment delay, or treatment discontinuation is permitted at the discretion of the treating investigator.

Toxicity	Grade (NCI CTCAE v4.0)	Temsirolimus Adjustment	Sorafenib Adjustment
HEMATOLOGIC			
Neutropenia	Grade 1 (ANC 1500 to < 2000/mm ³)	No change	No change
	Grade 2 (ANC 1000 to < 1500/mm ³)	No change	No change
	Grade 3 (ANC 500 to < 1000/mm ³)	Hold both drugs and recheck weekly until ≤ Grade 2, then decrease TEM by 1 DL and continue SOR at same dose; if recurs, hold both drugs and recheck weekly until ≤ Grade 2, then decrease SOR by 1 DL and continue TEM at same dose; continue alternating dose reductions if toxicity recurs	
	Grade 4 (ANC < 500/mm ³)	Hold both drugs and recheck weekly until ≤ Grade 2, then decrease both drugs by 1 DL	
Lymphopenia	Any Grade	No dose reductions or delays will be performed for lymphopenia	
Thrombocytopenia	Grade 1 (PLT 75,000 to < LLN/mm ³)	No change	No change
	Grade 2 (PLT 50,000 to < 75,000/mm ³)	No change	No change
	Grade 3 (PLT 25,000 to < 50,000/mm ³)	Hold both drugs and recheck weekly until ≤ Grade 2, then decrease TEM by 1 DL and continue SOR at same dose; if recurs, hold both drugs and recheck weekly until ≤ Grade 2, then decrease SOR by 1 DL and continue TEM at same dose; continue alternating dose reductions if toxicity recurs	
	Grade 4 (PLT < 25,000/mm ³)	Hold both drugs and recheck weekly until ≤ Grade 2, then decrease both drugs by 1 DL	
Anemia	Any Grade	No dose reductions or delays will be performed for anemia; transfusions and/or growth factor support may be used at the discretion of the investigator	
GASTROINTESTINAL (EXCLUDING HEPATIC DYSFUNCTION)			
Nausea/vomiting, constipation, or mucositis (despite optimal supportive care)	Grade 1	No change	No change
	Grade 2	No change	No change
	Grade 3	Hold both drugs until ≤ Grade 2, then decrease TEM by 1 DL and continue SOR at same dose; if recurs, hold both drugs until ≤ Grade 2, then decrease SOR by 1 DL and continue TEM at same dose; continue alternating dose reductions if toxicity recurs	
	Grade 4	Hold both drugs until ≤ Grade 2, then decrease both drugs by 1 DL	
Diarrhea (despite optimal supportive care)	Grade 1	No change	No change
	Grade 2	No change	No change
	Grade 3	Hold both drugs until ≤ Grade 2, then decrease SOR by 1 DL and continue TEM at same dose; if recurs, hold both drugs until ≤ Grade 2, then decrease TEM by 1 DL and continue SOR at same dose; continue alternating dose reductions if toxicity recurs	
	Grade 4	Hold both drugs until ≤ Grade 2, then decrease both drugs by 1 DL	

Toxicity	Grade (NCI CTCAE v4.0)	Temsirolimus Adjustment	Sorafenib Adjustment
HEPATIC DYSFUNCTION			
Hyperbilirubinemia (substitute direct bilirubin values and normal ranges for patients with Gilbert's Syndrome)	Grade 1 (BILT > ULN to 1.5 times ULN)	No change	No change
	Grade 2 (BILT > 1.5 to 3 times ULN)	Hold both drugs and recheck weekly until ≤ Grade 1, then decrease SOR by 1 DL and continue TEM at same dose; if recurs, hold both drugs and recheck weekly until ≤ Grade 2, then decrease TEM by 1 DL and continue SOR at same dose; continue alternating dose reductions if toxicity recurs	
	Grade 3 (BILT > 3 to 10 times ULN)	Hold both drugs and recheck weekly until ≤ Grade 1, then decrease both drugs by 1 DL	
	Grade 4 (BILT > 10 times ULN)	Discontinue protocol therapy	
Transaminase and alkaline phosphatase elevation (if assessed as treatment-related, clinically relevant, and ≥ 2 grades from baseline)	Grade 1 (> ULN to 2.5 times ULN)	No change	No change
	Grade 2 (> 2.5 to 5 times ULN)	No change	No change
	Grade 3 (> 5 to 20 times ULN)	Hold both drugs and recheck weekly until ≤ Grade 2, then decrease SOR by 1 DL and continue TEM at same dose; if recurs, hold both drugs and recheck weekly until ≤ Grade 2, then decrease TEM by 1 DL and continue SOR at same dose; continue alternating dose reductions if toxicity recurs	
	Grade 4 (> 20 times ULN)	Discontinue protocol therapy	
Ascites	Grade 1 (Asymptomatic)	No change	No change
	Grade 2 (Symptomatic, requiring diuretic)	No change	New ascites: Hold SOR and reevaluate weekly; if recovers to ≤ Grade 1, then decrease SOR by 1 DL; if recurs/worsens, decrease TEM by 1 DL; continue alternating dose reductions if toxicity recurs Worsening in baseline Grade 1 or 2 ascites: Optimize with supportive care including diuretic regimen as needed; if recurs/worsens, decrease SOR by 1 DL; if recurs/worsens, decrease TEM by 1 DL; continue alternating dose reductions if toxicity recurs

Toxicity	Grade (NCI CTCAE v4.0)	Temsirolimus Adjustment	Sorafenib Adjustment
	Grade 3 (Symptomatic, requiring paracentesis)	No change	
New ascites: Hold SOR and reevaluate weekly; if recovers to ≤ Grade 1, then decrease SOR by 1 DL; if recurs, decrease TEM by 1 DL; if recurs/worsens despite dose reductions in both drugs plus optimal supportive care, remove from study
 
Worsening in baseline Grade 1 or 2 ascites: Optimize with diuretic regimen and paracentesis if needed for symptoms; if repeat paracentesis is required after ≥ 2 weeks despite optimizing supportive care and diuretics, decrease sorafenib by 1 DL; if recurs/worsens, decrease TEM by 1 DL; if recurs/worsens despite dose reductions in both drugs plus optimal supportive care, remove from study

	Grade 4 (Life threatening)	Discontinue protocol therapy	

Toxicity	Grade (NCI CTCAE v4.0)	Temsirolimus Adjustment	Sorafenib Adjustment
CARDIOVASCULAR AND VASCULAR			
Hypertension	Blood Pressure (BP) ≤ 140/90	No change	
	BP >140/90 and ≤ 160/100	No change in study drugs; optimize anti-hypertensive regimen for goal BP ≤ 140/90; see section 6.1	
	BP > 160/100	If pre-treatment BP > 160/100, hold both drugs and treat according to Section 6.1; if BP remains > 160/100 despite optimal medical management , hold both drugs until ≤ 160/100, then decrease SOR by 1 DL; if HTN recurs with BP > 160/100, repeat and decrease SOR by 1 DL; if recurs again > 160/100, discontinue protocol therapy	
	Grade 4	Discontinue protocol therapy	
Hemorrhage	Grades 1, 2 (Mild, not requiring transfusion)	No change	No change
	Grade 3 (Requiring transfusion)	No change	Hold SOR until ≤ Grade 2, HCT stable for ≥ 1 week, bleeding resolved, and there is no known anatomic or pathologic condition that significantly increases risk of recurrent bleeding, then resume at same dose; if recurs, discontinue protocol therapy
	Grade 4 (Catastrophic or CNS)	Discontinue protocol therapy	
Arterial thrombosis, including myocardial ischemia or infarction, cerebrovascular accident, or mesenteric ischemia	Any Grade	Discontinue protocol therapy	
Venous thrombo-embolism* requiring anticoagulation (*excluding portal or hepatic vessel thrombosis or tumor thrombus)	Any Grade	Discontinue protocol therapy	
RENAL AND METABOLIC			
Elevated creatinine (despite optimal supportive care, i.e. hydration if dehydrated, and if assessed as treatment-related, clinically relevant, and ≥ 1 grade from baseline)	Grade 1 (CRE > ULN to 1.5 times ULN)	No change	No change
	Grade 2 (CRE > 1.5 to 3 times ULN)	Hold both drugs and recheck weekly until ≤ Grade 1, then resume at prior doses; if recurs, hold both drugs and recheck weekly until ≤ Grade 1, then decrease TEM by 1 DL and continue SOR at same dose; if recurs again, hold both drugs and recheck weekly until ≤ Grade 1, then decrease SOR by 1 DL and continue TEM at same dose; continue alternating dose reductions if toxicity recurs	
	Grade 3 (CRE > 3 to 6 times ULN)	Hold both drugs and recheck weekly until ≤ Grade 1, then decrease both drugs by 1 DL	
	Grade 4 (CRE > 6 times ULN)	Discontinue protocol therapy	
Hypo-phosphatemia	Grade 1	No change	No change
	Grade 2	No change	No change

Toxicity	Grade (NCI CTCAE v4.0)	Temsirolimus Adjustment	Sorafenib Adjustment

(despite optimal supportive care, i.e. electrolyte repletion)
	
Grade 3
	
Asymptomatic, first occurrence: Increase oral phosphate repletion regimen up to 3.5 grams per day as tolerated, encourage increased intake of phosphorus-rich foods, and continue study drug treatment. Recheck in 1 week. If \leq Grade 2, continue treatment at current study drug dosage with the increased phosphate repletion. If remains \geq Grade 3, hold TEM, continue SOR, and continue increased phosphate repletion. Recheck weekly until \leq Grade 2, then restart TEM with dose reduction by 1 DL and continue SOR at prior dose.
 
Asymptomatic, recurrent: If recurs after 1 dose level reduction in TEM despite continuing the highest tolerable dose of oral phosphate supplementation*, hold both drugs, continue repleting phosphate, and recheck weekly. Once recovers to \leq Grade 2, decrease SOR by 1 DL and continue TEM at prior dose. Continue this protocol with alternating drug dose reductions if asymptomatic Grade 3 toxicity recurs.
 
*If asymptomatic Grade 3 hypophosphatemia recurs but patients have not been taking the highest tolerable dose of oral phosphate supplementation, follow the hypophosphatemia algorithm above as for the first occurrence of asymptomatic grade 3 hypophosphatemia.
 
Symptomatic, first occurrence: Increase oral phosphate repletion regimen up to 3.5 grams per day as tolerated, encourage increased intake of phosphorus-rich foods, and hold both TEM and SOR. Consider cautious intravenous phosphate supplementation at the investigator's discretion and according to standard institutional protocols. Recheck weekly until \leq Grade 2 and asymptomatic, then decrease TEM by 1 DL and resume SOR at prior dose.
 
Symptomatic, recurrent: If recurs after 1 DL reduction in TEM and despite continuing the highest tolerable dose of oral phosphate supplementation*, hold both drugs and continue repleting phosphate. Consider cautious intravenous phosphate supplementation at the investigator's discretion and according to standard institutional protocols. Recheck weekly. Once recovers to \leq Grade 2 and asymptomatic, decrease SOR by 1 DL and continue TEM at prior dose. Continue this protocol with alternating drug dose reductions if toxicity recurs. *If symptomatic Grade 3 hypophosphatemia recurs but patients have not been taking the highest tolerable dose of oral phosphate supplementation, follow the hypophosphatemia algorithm above as for the first occurrence of symptomatic grade 3 hypophosphatemia.
	
	
Grade 4 (< 1.0 mg/dL)
	
Follow protocol above for symptomatic Grade 3 hypophosphatemia.
	

Hyperglycemia
	
Grade 1
	
No change
	
No change

Toxicity	Grade (NCI CTCAE v4.0)	Temsirolimus Adjustment	Sorafenib Adjustment
(despite optimal supportive care)	Grade 2	No change	No change
	Grade 3	Hold TEM and recheck weekly until ≤ Grade 2, then decrease by 1 DL	No change
	Grade 4	Discontinue protocol therapy	
Hyperlipidemia (despite optimal supportive care)	Grade 1	No change	No change
	Grade 2	No change	No change
	Grade 3	Hold TEM and recheck weekly until ≤ Grade 2, then decrease by 1 DL	No change
	Grade 4	Hold TEM and recheck weekly until ≤ Grade 2, then decrease by 1 DL	No change
DERMATOLOGIC			
Hand-foot syndrome (despite optimal supportive care)	Grade 1 (Numbness, discomfort, dysesthesia/paresthesia, tingling, painless swelling, or erythema that does not disrupt normal activities)	No change	No change
	Grade 2 (Painful erythema, swelling, or discomfort that disrupts normal activities)	No change	Hold SOR until ≤ Grade 1, then resume at prior dose; if recurs, hold SOR until ≤ Grade 1, then decrease by 1 DL
	Grade 3 (Moist desquamation, ulceration, blistering, or severe pain that disrupts ADL)	No change	Hold SOR until ≤ Grade 1, then decrease by 1 DL
	Grade 4	Discontinue protocol therapy	
Other dermatologic toxicity (including dermatitis, non-healing wound, pruritis, desquamation) (despite optimal supportive care)	Grade 1	No change	No change
	Grade 2	No change	Hold SOR until ≤ Grade 1, then resume at prior dose; if recurs, hold SOR until ≤ Grade 1, then decrease by 1 DL
	Grade 3	Hold both drugs until ≤ Grade 1, then reduce SOR and/or TEM by 1 DL based upon the investigator's attribution of toxicity	
	Grade 4	Discontinue protocol therapy if severe or life-threatening toxicity, versus apply modification for Grade 3	
OTHER			
Other toxicities* (despite optimal supportive care)	Grade 1	No change	No change
	Grade 2	No change	No change
	Grade 3	Hold both drugs until ≤ Grade 1, then reduce SOR and/or TEM by 1 DL based upon the investigator's attribution of toxicity	
	Grade 4	Discontinue protocol therapy if severe or life-threatening toxicity, versus apply modification for Grade 3	

*For any toxicity (regardless of grade), despite optimal supportive care, that is felt by the treating investigator to represent a risk to the patient's safety, additional dose reduction, treatment delay, or treatment discontinuation is permitted at the discretion of the treating investigator.

